### Changes due to the impact of COVID-19:

We hypothesize that the case mix of the "pandemic period" cohort is likely to be different to the case mix seen during "non-pandemic" times. This includes a potential increase in the average severity of disease in those children presenting at the facility. We are requesting support for the addition of a pandemic phase in Phase 1 – the baseline observational component of PRST. This will include a 25% increase in sample size at each experimental site (250 additional participants per experimental site). This increase in sample size is critical to developing a risk stratification model that is robust during pandemic and non-pandemic times.

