#### **Outcomes Analysis**

We will compare the proportion of children at the two intervention sites receiving a completed bundle within 60 minutes to the historical and the contemporaneous control group (Marascuillo procedure). The median time to an appropriate bundle of care will be compared using a Mann–Whitney U test. The triage prioritization between the phases and the proportion of children who received and appropriate bundle of care within each triage categorization will be compared with Fisher's exact tests. Segmented regression analysis of the interrupted time series of the pre- and post- intervention periods will be used to assess immediate effects and effects over time, controlling for prior trends that may continue without our intervention. Quantile regression will be used to estimate the median differences. We will compare the estimated times at end of the intervention period with the expected counterfactual value, had the pre-intervention trend continued as if the intervention never occurred. We will compare the time to event (treatment bundle) using the Kaplan-Meier estimator with censure at 180 minutes. Secondary outcomes will be compared using generalized estimating equations.

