### Outcomes

#### Primary outcomes

**For model development** Hospital admission (within 5 days of assessment) status determined from hospital records, and a follow up call 7 days post discharge. This will inform development of a clinical prediction model based on need for hospital admission.

For effectiveness evaluation of digital triage tool An increase of at least 20% in the proportion of critically ill children (emergency and priority cases) receiving an appropriate bundle of care within 60 min of arrival at the hospital. An appropriate bundle of care is defined as at

least one of antibiotics, intravenous fluids, or oxygen as appropriate for age and clinical syndrome as determined and administered by **hospital staff**.

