#### **Outcomes** analysis

We will be conducting our primary analysis using a difference in differences method. For our primary analysis, a logistic regression model for receipt of bundle of care within 1 h will be fit including: 1) phase of study (pre vs. post PRST) and 2) group (intervention versus control) as independent dummy variables and 3) their interaction. The interaction term corresponds to the difference in log-odds between groups in baseline vs intervention and it's exponent as the ratio of odds ratios. We will summarise this difference by estimating the marginal effect (risk difference) of phase in both the control and intervention groups. The difference of these marginal effects is the so-called 'difference in difference' for a binary outcome [24]. Confidence intervals will be based on the delta-method, or bootstrapping, where appropriate. A similar approach will be used for binary secondary outcomes (mortality, readmission), or quantile regression for median time to bundle of care, a non-parametric outcome.

Subgroup analyses specified a priori include Ugandan vs. Kenyan intervention site, young infant (under 2 months old) vs. children under 5 vs. older children, and presentation during day-shift hours versus night-shift hours (if applicable). We will also perform subgroup analyses on each triage category (emergency, priority, queue); patients from the pre-intervention phase will be retroactively categorized into these subgroups for this analysis. These subgroup analyses will be conducted with the inclusion of a three-way interaction between said variable, phase, and group. Statistical significance will be based on a likelihood ratio test comparing models with and without this term. This three-way interaction term would represent potential interactions between different subgroups and our difference in odds ratio obtained in our primary analysis, and results will again be presented on the risk difference scale based on marginal effects. This method of subgroup analysis sometimes termed a difference in difference in differences method.

Although none are expected, if there are any time varying confounders identified during the study that differ between intervention and control (health system or policy changes, natural events, changes in patient populations etc.) they will be included in above models as sensitivity analyses.

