As we are continually collecting data regarding predictors for admission alongside the clinical team, there is the possibility that our research activities may interact with the efficiency of delivering the sepsis bundle of care. Although the possibility of such interaction is minimized by our use of dedicated research personnel who would not approach patients who are actively receiving clinical care, any such interactions could potentially limit the external validity of our study to non-researchcontrolled settings. Therefore, to assess this potential interaction, we will pause the collection of predictor data 1 month before and after implementation of the PRST program. This pause will also occur in the control group in order to replicate any bias caused by changes in our primary outcome attributable to the pause rather than the PRST program. To investigate the potential for this bias, we will treat the collection or non-collection of predictors as a dummy variable for subgroup analysis using the difference in difference in differences method described above.

All analyses will be conducted using R statistical software [25], and an alpha level of 0.05 will be considered statistically significant for all outcome analyses.

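### The primary-outcome analyses state no allowance for correlation among children seen at the same hospital on the same day, so their standard errors are too small if that correlation is positive.

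*Combined protocol and SAP*

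**What the plan says.** Two texts describe the analysis, and they differ.

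The published protocol paper (Statistical analysis, Outcomes analysis) fits a logistic model at child level with phase, group and their interaction. On precision it says only: "Confidence intervals will be based on the delta-method, or bootstrapping, where appropriate". For subgroup interactions it says: "Statistical significance will be based on a likelihood ratio test comparing models with and without this term". To study the pause in predictor collection, it will "treat the collection or non-collection of predictors as a dummy variable for subgroup analysis". It adds that "an alpha level of 0.05 will be considered statistically significant for all outcome analyses". The paper's primary outcome is a rise by a fifth or more "in the proportion of critically ill children (emergency and priority cases) receiving an appropriate bundle of care within 60 min of arrival", but the model description does not restrict the analysis to those children.

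Protocol v5.0 (section 17, Outcomes Analysis) compares the proportion of children "receiving a completed bundle within 60 minutes to the historical and the contemporaneous control group" by the Marascuilo procedure, and median time by a Mann-Whitney test. It also names quantile regression for median differences, and says: "Segmented regression analysis of the interrupted time series of the pre- and post- intervention periods will be used to assess immediate effects". The unit of that regression (child, day or week) is not given. Generalized estimating equations are named for secondary outcomes only.

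Neither text names a day or cluster term, a random effect, a robust variance or a resampling unit for the primary outcome. Neither sample size section has a design effect.

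**The concern.** Time to treatment depends on conditions that children attending on the same day share. Appendix A of v5.0 (Clinical Timekeeper) codes delay as due to stock-outs or to every health worker being occupied. The Study Setting section describes Kenyan outpatient departments with one or two triage nurses, who also give treatment. Several children are sampled per shift. Positive same-day correlation is therefore plausible, though the documents do not measure it.

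It does not cancel in the contrast of interest. Every hospital-day belongs to one phase and one group, so day-to-day variation adds variance to each of the four cells of the difference-in-differences, and equally to a before-after comparison. The delta method on an ordinary logistic fit, a bootstrap of children, and the Marascuilo and Mann-Whitney tests all omit it. Likelihood-ratio tests are affected in the same way for interaction terms that are constant within a day, namely site and predictor collection on or off. No claim is made for age group, triage category or day versus night shift, which vary within a day.

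If the correlation is positive, the 0.05 level is exceeded, and a run of good or bad days can be read as an effect of the tool.

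**Working it through.** **Inputs from the documents**
- Level 0.05. Two-sided is assumed, as the sidedness is not stated.
- Baseline proportion 27%.
- Target of 4000 per site, with a minimum of 1000 in Phase I; accrual described over six months (182.5 days).
- For v5.0: "This will include a 25% increase in sample size at each experimental site (250 additional participants per experimental site"), which implies 1000 + 250 = 1250 per experimental site in Phase I.

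**Assumptions, not in the documents**
- Same-day intraclass correlation (ICC) of 0.02 to 0.10. Each nurse enrols a child every 35-50 minutes, which argues for the lower end.
- 30% of enrolled children are emergency or priority cases.

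**Enrolled per hospital-day**
- 1000/182.5 = 5.5
- 1250/182.5 = 6.8
- 4000/365 = 11 (target spread over two six-month phases)
- 4000/182.5 = 22 (whole target inside one phase)

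Taking 30% gives m = 1.65, 2.05, 3.3 and 6.6 analysed children per day.

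**Formulas**
- Equal daily counts: DEFF = 1 + (m − 1) × ICC.
- Poisson daily counts: DEFF = 1 + m × ICC.
- True error of a nominal 5% test: 2 × (1 − Φ(1.96/√DEFF)).

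The plan's own figure is recovered first: at ICC = 0, DEFF = 1 and the error is 0.05. Worked example at m = 3.3, ICC 0.10, equal counts: DEFF = 1.23, √DEFF = 1.109, 1.96/1.109 = 1.767, error 7.7%. With Poisson counts DEFF = 1.33 and the error is 8.9%.

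**Simulation.** 60,000 runs per setting; two groups by two phases; 182 days per cell; Poisson counts; beta-binomial days; p = 0.27; no true effect; no site-by-period variation.

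| Analysed per day | Equal counts, ICC 0.02 / 0.10 | Poisson formula | Simulation |
|---|---|---|---|
| 1.65 | 5.2% / 5.8% | 5.4% / 6.9% | 5.5% / 7.1% |
| 2.05 | 5.2% / 6.2% | 5.5% / 7.4% | 5.3% / 7.5% |
| 3.3 | 5.5% / 7.7% | 5.8% / 8.9% | 5.8% / 9.0% |
| 6.6 | 6.3% / 11.7% | 6.5% / 12.8% | 6.5% / 12.4% |
| 11 | 7.4% / 16.6% | 7.6% / 17.6% | 7.6% / 17.4% |
| 22 | 10.0% / 26.6% | 10.2% / 27.3% | 10.1% / 27.1% |

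A repeat simulation gave 5.4% / 7.2% at 1.65 per day and 7.4% / 18.4% at 11. If all enrolled children are analysed at minimum enrolment (5.5 per day), the equal-count formula gives 6.0% / 10.4%.

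**Does day clustering help?** In the same settings, errors clustered on hospital-day rejected 4.9-5.2% of the time (4.7-5.7% in the repeat). In a bootstrap check (8,000 runs, 400 resamples, 2.05-6.6 per day, ICC 0.05-0.10), resampling children gave 7.0-13.2% and resampling days 5.0-6.1%.

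**What it leaves.** These results assume no variation between sites over time. With an assumed site-by-period standard deviation of 0.1 on the logit scale, the day-clustered test still rejects 11-12%, 15-18% and 21-26% at 1.65, 3.3 and 6.6 per day. At 0.05 the figures are 6.3-6.8%, 7.5-8.4% and 9.1-11.1%.

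**The case against.** **The size is assumed and may be small.** This stands. Neither the ICC nor the emergency/priority share is in the documents. At minimum enrolment with ICC 0.02 the excess is a few tenths of a point. Fixed time cut-offs also make daily counts steadier than Poisson: with exactly 5.5 enrolled per day, a 30% share and ICC 0.10, DEFF = 1 + 4.5 × 0.3 × 0.10 = 1.135 and the error is 6.6%, against 6.9% with Poisson counts.

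**The largest figures rest on a doubtful reading.** This also stands. A reader might infer that the true error is near 27%. That needs 22 analysed children every day, so the whole 4000 inside one six-month phase with all of them analysed. At 35-50 minutes each, 22 children take about 13-18 study-nurse hours a day, every day. The text reads at least as naturally as a site total over both phases.

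**Bootstrapping could mean resampling days, and segmented regression could be run on aggregates.** True, and a day bootstrap would be valid. A reader should not infer that the plan rules these out. But neither is stated, and the delta method and the two named v5.0 tests are too narrow under positive correlation when carried out as written. Time-varying confounders as sensitivity analyses address identified shared events, not random day-to-day variation.

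**The bigger threat is one or two hospitals per group.** Agreed. A reader might infer that day clustering secures the 5% level; it does so only if there is no site-by-period variation. That is a reason to state the limitation, not to leave a removable error in place.

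**The paper's model may not govern.** It was published in June 2020; v5.0 is dated October 2020 and adds Gulu as a control site. The four-cell layout simulated may not be the one used. The variance argument applies to either text.

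**Conclusion.** The point holds conditionally. As written, the primary-outcome analyses in both texts treat children as independent or leave the unit open, and their standard errors are too small if same-day correlation is positive. For an assumed ICC of 0.02-0.10, the nominal 5% error is about 5-7% at 1.65 analysed children per day (1000 enrolled in six months, assumed 30% emergency or priority), about 6-9% at 3.3 per day, and about 7-18% at 11 per day. Going beyond that range requires 4000 per site within one six-month phase.

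The documents do not support saying that the 0.05 level is badly breached, since the correlation is unmeasured and the excess could be negligible. Nor do they support saying that every subgroup test is affected, or that v5.0 needs a new primary model. The change is worth making because it is cheap and does little harm if the correlation is near zero.

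**What to change.** For the 60-minute bundle comparison, specify a variance clustered on hospital-day, or a bootstrap that resamples hospital-days within site and phase. Use the same day-level resampling for the quantile regression of time. Repeat with week blocks as a sensitivity analysis. For interaction terms constant within a day (site; predictor collection on or off), use Wald tests on that variance in place of likelihood-ratio tests.

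If v5.0 governs:
- keep the named comparison of proportions, but replace each binomial variance with the day-clustered one;
- take inference on median time from the quantile regression already named there, with a day bootstrap, rather than from the Mann-Whitney test;
- run the segmented regression on day or week aggregates, or with the same clustered errors.

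State that this removes only the within-day part and gives no protection against site-by-period variation with one or two hospitals per group.

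Cost: a short change to the analysis plan and some programming. No new data are needed, since the study team holds the recruitment date. The shared dataset will carry only the month, so outside users could not make this correction later. Intervals will be somewhat wider.

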### Changes due to COVID-19

The global COVID-19 has introduced many challenges to the successful completion of this project. We have been unable to initiate Phase I of the project in Nairobi, Kenya due to restrictions implemented to reduce the risk of spread of COVID-19. We have made good progress in recruitment in Jinja, Uganda. I consultation with our investigators, implementation partners and funders we have decided to add an additional site at Gulu Regional Hospital in Uganda. Gulu Regional Referral Hospital will serve as a control site while the intervention phase (Phase III) takes place at Jinja Regional Referral Hospital. Once the intervention period has been completed in Jinja, the intervention will be introduced at Gulu Regional Referral Hospital.

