#### Study sites

- 1. Jinja Regional Referral Hospital, Jinja, Uganda (experimental site)
- 2. Mbagathi County Hospital, Nairobi, Kenya (experimental site)
- 3. Kiambu County Referral Hospital, Nairobi, Kenya (control site)

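### In the published protocol, the Ugandan-versus-Kenyan site subgroup test has zero degrees of freedom in the usual hierarchical model, because that design has no Ugandan control hospital

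*Combined protocol and SAP*

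**What the plan says.** The specification is in the published protocol, under Outcomes analysis. The primary model is a logistic regression for receipt of the bundle within one hour, with "1) phase of study (pre vs. post PRST) and 2) group (intervention versus control) as independent dummy variables and 3) their interaction". The country comparison is the first subgroup listed: "Subgroup analyses specified a priori include Ugandan vs. Kenyan intervention site". The method is the same for all subgroups: "These subgroup analyses will be conducted with the inclusion of a three-way interaction between said variable, phase, and group". The decision rule is: "Statistical significance will be based on a likelihood ratio test comparing models with and without this term". No exception is made for the country comparison, and the lower-order subgroup terms are not listed.

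Under Study sites, the same paper lists three hospitals:

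- "Jinja Regional Referral Hospital, Jinja, Uganda (experimental site")
- "Mbagathi County Hospital, Nairobi, Kenya (experimental site")
- "Kiambu County Referral Hospital, Nairobi, Kenya (control site")

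Its section on Phase I says that Kiambu stays in baseline data collection for an extended period, so it can supply control data for both calendar phases.

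Protocol version 5.0 differs on two points. Section 8 (changes due to COVID-19) adds a Ugandan control: "Gulu Regional Referral Hospital will serve as a control site while the intervention phase (Phase III) takes place at Jinja Regional Referral Hospital". Section 17 (Outcomes Analysis) sets out a different analysis, with no difference-in-differences model, no three-way term and no country subgroup.

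**The concern.** A three-way interaction with phase and group asks whether the difference-in-differences is larger in one stratum than in the other. That needs intervention and control children in both strata and both phases. For country, the published design has intervention hospitals in Uganda and Kenya but a control hospital only in Kenya, so the Ugandan difference-in-differences has no Ugandan control change to subtract.

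At stake is the only test in these documents of whether the effect on timely treatment differs between the Ugandan and Kenyan sites. The published Discussion itself expects performance of the tool to vary with geography. An analyst who follows the text would find the term dropped by the software. The analyst would then have to choose a replacement after seeing data, for a subgroup declared in advance.

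**Working it through.** The plan states no degrees of freedom for this test, so there is no figure to reproduce. The check counts the independent columns of the design matrix over the cells that the design can fill.

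**Inputs.** Sites and roles come from Study sites in the published protocol; the model, term and test come from its Outcomes analysis. Code phase p (0 pre, 1 post), group g (1 intervention, 0 control) and country c (1 Uganda, 0 Kenya). Kiambu's data during the intervention calendar period count as post.

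| Hospital | Cells (p, g, c) |
|---|---|
| Jinja | (0,1,1), (1,1,1) |
| Mbagathi | (0,1,0), (1,1,0) |
| Kiambu | (0,0,0), (1,0,0) |
| Ugandan control | (0,0,1), (1,0,1): both empty |

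That fills 6 of 8 cells.

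**Step 1: aliasing.** Wherever c = 1, g = 1. So g×c = c and p×g×c = p×c in every filled cell.

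**Step 2: ranks.** Test df = rank(with the three-way term) minus rank(without it).

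- Without it: 1, p, g, c, p×g, p×c, g×c. Seven columns, one redundant (g×c = c): rank 6.
- With it: eight columns, two redundant (g×c = c and p×g×c = p×c): rank 6.
- df = 6 − 6 = 0.

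With all 8 cells filled the ranks would be 8 and 7, so df = 1. The primary model (1, p, g, p×g) has full rank 4 in the published design.

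**Step 3: fitted check.** A simulated logistic fit with 1,000 children in each of the 6 cells, dropping redundant columns, gave a log-likelihood of −3671.345 for both models and a likelihood-ratio statistic of 0.0. The gap is structural, so a larger sample does not change it.

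**Step 4: the route to 1 df.** If country by phase is left out of both models, the base (1, p, g, c, p×g) has rank 5. Adding p×g×c gives rank 6, so df = 1. That six-parameter model is saturated, and the added coefficient equals (post minus pre at Jinja) minus (post minus pre at Mbagathi) in log-odds. It is a site by phase comparison and takes nothing from the control.

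**Step 5: the contrast without a control cell.** Write Δ for a post-minus-pre change. With Kiambu as the common control,

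(Δ Jinja − Δ Kiambu) − (Δ Mbagathi − Δ Kiambu) = Δ Jinja − Δ Mbagathi.

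This holds on the log-odds and the risk-difference scale. Among the two intervention hospitals, site by phase has ranks 4 with and 3 without the interaction, so df = 1.

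**Step 6: if the subgroup were carried into version 5.0.** The updated timeline table in Section 7 is broken in the text available, so when Gulu and the Kenyan hospitals contribute data is an assumption. The range is:

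| Data available | Rank with | Rank without | df |
|---|---|---|---|
| Jinja and Gulu only, both phases | 4 | 4 | 0 |
| Jinja both phases; Gulu post only; Mbagathi and Kiambu baseline only | 5 | 5 | 0 |
| Jinja, Mbagathi and Kiambu both phases; Gulu post only | 7 | 7 | 0 |
| All four hospitals, both phases | 8 | 7 | 1 |

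**The case against.** The strongest reply is that the plan never says the model is hierarchical. It asks for a three-way term and a test with and without it, and it defines the variable among intervention sites. On that reading country by phase need not be in the model, the test has 1 df, and it answers the intended question. The arithmetic of this reply stands. What does not follow is that the plan specifies such a model. Keeping the lower-order terms is the usual convention, and nothing in the text says to drop one. The two readings give 0 df and 1 df, so the choice has to be written down.

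The importance should also be kept in proportion. This is one of several subgroup analyses. The failure would show itself, because the software would report the term as not estimable; no false p-value would result. The published protocol mentions malaria prevalence in Jinja when discussing recalibration of the prediction model, and does not give it as the reason for this subgroup. With one intervention hospital per country, any model compares two hospitals. All of this stands.

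A reader might infer two stronger conclusions that the documents do not support:

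- **That the Ugandan-versus-Kenyan question cannot be tested at all.** Step 5 gives a 1-df test from the data already planned.
- **That the defect runs through all the documents.** Version 5.0 adds a Ugandan control, still describes Mbagathi in Phase III and Kiambu as control, and contains no three-way test. Whether the term would be estimable in that design depends on which hospitals supply which phases.

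**Conclusion.** The concern holds for the published protocol. Under the usual hierarchical model, the specified test for the Ugandan-versus-Kenyan intervention-site subgroup has 0 df (rank 6 with and without the term) and yields no estimate or p-value. This rests on two things: the site list in that paper, with Kiambu as the only control, and a model that keeps the lower-order terms.

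The defect is confined to this subgroup. It deserves correction because the comparison was declared in advance and would otherwise be replaced by a choice made during analysis.

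For version 5.0 the conclusion is conditional. The three-way term would be estimable only if Gulu contributes control data in both phases and Jinja, Mbagathi and Kiambu also have both. Section 8 describes Gulu as a control during Phase III at Jinja; whether usable Gulu data from before that point will exist cannot be settled from the broken timeline table.

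**What to change.** For this subgroup only, replace the three-way term in Outcomes analysis of the published protocol with a site by phase contrast among the intervention hospitals: (post minus pre at Jinja) minus (post minus pre at Mbagathi). Test it with a 1-df likelihood-ratio test of site by phase, and report it on the risk-difference scale with the interval methods already planned. State that the Kiambu change cancels because Kiambu is the common control.

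State two limits beside the result. It is a difference between two hospitals, so country and hospital cannot be separated. It also cannot separate a difference in tool effect from a Uganda-specific time trend, because no Ugandan control measures that trend.

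Keep the three-way model for age, shift and triage category, which can occur in both the intervention and control groups.

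If the subgroup is carried into the version 5.0 design, add two conditions:

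- Use the three-way term only if Gulu, Kiambu, Jinja and Mbagathi all have data in both phases. Until Mbagathi has both phases, state that the Jinja-versus-Mbagathi contrast is not estimable.
- If Jinja and Mbagathi have different controls, the control changes do not cancel. Set each site's change against its own control, (Δ Jinja − Δ Gulu) − (Δ Mbagathi − Δ Kiambu), or report the two-site contrast as uncontrolled.

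The cost is a few sentences in the analysis plan. The replacement needs no data beyond what the published design already collects.
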